Treatment conducted as part of this study may be of benefit to an individual participant (e.g. progress on cognitive testing over time). The main sharing of study results, however, will be with the general public and medical community which may benefit from our study outcome. We plan to report our findings in published material and at medical conferences. Data sharing will follow the TBIMS protocol.

XIV. Safety and Adverse Events

Each subject will be followed medically daily by their rehabilitation resident and attending physicians and have 24 hour monitoring by rehabilitation nursing. The research assistant at each site will check in with the patient/LAR and nursing staff daily Monday through Friday to elicit any concerns. [name]. a psychiatrist in the University of Washington's Department of Rehabilitation Medicine has expertise in TBI treatment and research procedures and has agreed to be the Data Safety Monitor (DSM). He will receive a quarterly summary of all Adverse Events for review and will be contacted by the study team within 24 hours of any Serious Adverse Event to review with the study physician. Any serious adverse event will be reported to the Human Subjects Division as well immediately. At quarterly intervals after subject enrollment begins, the DSM will review and evaluate the studies' clinical efficacy and safety data. The DSM will monitor study progress, examine adverse events (AEs) and serious adverse events (SAEs), and recommend the continuation without change, suspension, or termination of a study.

XV. Definitions

Unanticipated Problems Involving Risk to Subjects or Others

Any incident, experience, or outcome that meets all of the following criteria:

- Unexpected in nature, severity, or frequency (i.e. not described in study-related documents such as the IRB-approved protocol or consent form, the investigators brochure, etc)
- Related or possibly related to participation in the research (i.e. possibly related means there is a reasonable possibility that the incident experience, or outcome may have been caused by the procedures involved in the research)
- Suggests that the research places subjects or others at greater risk of harm (including physical, psychological, economic, or social harm).

Adverse Event

An *adverse event* (AE) is any symptom, sign, illness or experience that develops or worsens in severity during the course of the study. Intercurrent illnesses or injuries should be regarded as adverse events. Abnormal results of diagnostic procedures are considered to be adverse events if the abnormality results in study withdrawal, is associated with a serious adverse event, is associated with clinical signs or symptoms, or is considered by the investigator to be of clinical significance.

Serious Adverse Event

Adverse events are classified as serious or non-serious. A **serious adverse event** is any AE that is: fatal, life-threatening, prolongs hospital stay, results in persistent or significant disability or incapacity, a congenital anomaly or birth defect, or an important medical event.

All adverse events that do not meet any of the criteria for serious should be regarded as **non-serious adverse event**.

Important medical events are those that may not be immediately life threatening, but are clearly of major clinical significance. They may jeopardize the subject, and may require intervention to prevent one of the other serious outcomes noted above.

Adverse Event Reporting Period

The study period during which adverse events must be reported is normally defined as the period from the initiation of any study procedures to the end of the study treatment follow-up. For this study, the study treatment follow-up is defined as 2 days following the last study treatment (Day 15).

Hospitalization

Subjects will be hospitalized patients receiving care for their recent traumatic brain injury. Therefore, hospitalization is a requirement to be a part of this study, and will not be included as an adverse event for this study.

XVI. Recording of Adverse Events

At each contact with the subject, the study staff must seek information on adverse events by specific questioning. Information on all adverse events should be recorded immediately in the source document, and also in the appropriate adverse event module of the case report form (CRF). All clearly related signs, symptoms, and abnormal diagnostic procedures results should recorded in the source document, though should be grouped under one diagnosis.

All adverse events occurring during the study period must be recorded. The clinical course of each event should be followed until resolution, stabilization, or until it has been determined that the study treatment or participation is not the cause. Serious adverse events that are still ongoing at the end of the study period must be followed up to determine the final outcome. Any serious adverse event that occurs after the study period and is considered to be possibly related to the study treatment or study participation should be recorded and reported immediately.

Minimum information required for each AE includes type of event, duration (start and end dates), severity, seriousness, causality to study, action taken, and outcome.

Evaluating Adverse Events

Assessment should include the intensity (severity) of the event and the relationship to Study Intervention(s).

Severity of AEs will be graded by the Investigator using the following criteria as guidelines:

- 1) **Mild:** Nuisance, barely noticeable.
- 2) **Moderate:** Uncomfortable, troublesome symptoms not significantly interfering with daily activities or sleep.
- 3) **Severe:** Symptoms significantly interfere with daily activities or sleep.

The relationship of the AE to the study treatment should be specified by the Investigator, using the following definitions:

- 1) **Not Related:** Concomitant illness, accident or event with no reasonable association with treatment.

- 2) **Unlikely:** The reaction has little or no temporal sequence from administration of the study treatment, and/or a more likely alternative etiology exists.
- 3) **Possibly Related:** The reaction follows a reasonably temporal sequence from administration of the treatment and follows a known response pattern to the suspected treatment; the reaction could have been produced by the study treatment or could have been produced by the subject's clinical state or by other modes of therapy administered to the subject.
- 4) **Probably Related:** The reaction follows a reasonable temporal sequence from administration of study treatment; is confirmed by discontinuation of the study treatment or by rechallenge; and cannot be reasonably explained by the known characteristics of the subject's clinical state.
- 5) **Definitely Related:** The reaction follows a reasonable temporal sequence from administration of study treatment; that follows a known or expected response pattern to the study treatment; and that is confirmed by improvement on stopping or reducing the dosage of the study treatment, and reappearance of the reaction on repeated exposure.

Notifying the Principal Investigator

Any study-related unanticipated problem posing risk of harm to subjects or others that are not Adverse Events should be reported on the "*Unanticipated Problems Form*". Any type of serious adverse event, must be reported to the site Principal Investigator or designee within 1 business day of the event. Within the following 48 hours, the investigators must provide further information on the serious adverse event or the unanticipated problem in the form of a written narrative. This should include a copy of the completed Serious Adverse Event form, and any other diagnostic information that will assist the understanding of the event.

Notifying the Local IRB

At the University of Washington, [name] or [name] will be responsible for safety reporting to the IRB and complying with their reporting requirements. The other sites for this project will have an investigator who is responsible for safety reporting to their local IRBs. Copies of each report and documentation of IRB notification and receipt will be kept in the locked secured study file.

Notifying the Data Safety Monitor

Unanticipated problems posing risks to subjects or others and serious adverse events associated with the research will be forwarded to the Data Safety Monitor of the study at the University of Washington, within 24 hours.

Stopping Rules

There are no planned interim or futility analyses. The Data Safety Monitor may recommend stopping for safety based on overall study review.

Independent Data Safety Monitor

The Data Safety Monitor is required to review all unanticipated problems involving risk to volunteers or others, serious adverse events and all volunteer deaths associated with the protocol and provide an unbiased written report. At a minimum the Data Safety Monitor should comment on the outcomes of the event or problem and in the case of a serious adverse event or death comment on the relationship to participation in the study. The Data Safety Monitor should also indicate whether he concurs with the details of the report provided by the study investigator.

XVII. Ethical Considerations/Protection of Human Subjects

Ethical Conduct of the Study

This study is to be conducted according to US and international standards of Good Clinical Practice (FDA Title 21 part 312 and International Conference on Harmonization guidelines), applicable government regulations and Institutional research policies and procedures.

Institutional Review Board (IRB)

This protocol and any amendments will be submitted to a properly constituted Institutional Review Board (IRB), in agreement with local legal prescriptions, for formal approval of the study conduct. The decision of the IRB concerning the conduct of the study will be made in writing to the investigator.

Subject Information and Informed Consent

This study will be conducted in compliance with Title 45 Part 46 of the CFR pertaining to informed consent. At the first visit, subjects will give their written consent to participate in the study after having been informed about the nature and purpose of the study, participation/termination conditions, risks, and potential benefits. Informed consent is a process that is initiated prior to the individual's or proxy's agreeing to participate in the study and continuing throughout the individual's study participation. Extensive discussion of risks and possible benefits of this therapy will be provided to the participants and their families. Consent forms describing in detail the Study Agent(s)/Intervention(s) study procedures and risks are given to the participant/proxy and written documentation of informed consent is required prior to starting study agent/intervention. Consent forms will be IRB approved and the participant/proxy will be asked to read and review the document. Upon reviewing the document, the investigator will explain the research study to the participant/proxy and answer any questions that may arise. The participants/proxies should have sufficient opportunity to discuss the study and process the information in the consent process prior to agreeing to participate. The participants/proxies may withdraw consent at any time throughout the course of the study. A copy of the informed consent document will be given to the participants/proxies for their records. The rights and welfare of the participants will be protected by emphasizing to them that the quality of their medical care will not be adversely affected if they decline to participate in this study.

Sample Characteristics that Raise Special Concerns

Participants may not be sufficiently able to independently provide informed consent. We will have proxy consent forms for the subject and the Legally Authorized Representative (LAR) in this case. Decision making capacity assessment is described in the above study procedure narrative. We do not anticipate re-consenting subjects as the study duration is only 10 days of intervention.

XVIII. Potential Risks, Potential Benefits, Intent to Benefit, and Risk/Benefit Ratio

Potential risks

Subjects may experience an adverse reaction to the active or comparison treatment; significant adverse reactions are unlikely given literature on these light therapy interventions in a variety of populations. The intervention involves exposure to light, which can be bright and which some participants may find bothersome. Side effects of the bright white light are generally mild and subside but can include hypomania, irritability, headache, nausea, eye strain or vision changes and sleep changes (Chang AM, 2012). Other side effects are not anticipated given the study target population and the study team's experience with sleep changes after TBI and light therapy. Other study procedures including the questions about cognition such as memory may be uncomfortable either physically or emotionally and will be approached respectfully and confidentially. The placement of the Actiwatch on the wrist will result in contact with the skin, and like any watch, could result in contact dermatitis. Contact Dermatitis is readily treated with skin lotion and may involve repositioning the device. Prior studies have not reported this as a problem.

As with any study, there is also a remote chance that an outside party may discover a participant's identity and participation in the study. Risk of physical harm or injury is unlikely given the mild nature of reported side effects in the literature regarding light exposure and the non-invasive nature of actigraphy. No risk to study personnel is anticipated.

Alternative common treatments for insomnia include sedative drugs / sleep medications, behavioral interventions and environmental modifications. These other interventions will be recorded and will not be blocked during this study.

Protection Against Risk

1. We will have a Data Safety Monitor who is independent of the study to review regular reports of any reported related or unrelated adverse events as noted above. All serious adverse events will be reported within 24 hours to him as well as to the IRB, [name] and site PIs. Our DSM will be able to halt recruitment until any adverse events are thoroughly explored. A summary of all adverse events will be generated quarterly.
2. Subjects will be interviewed in private settings, will be counseled that they may refuse to answer any question, and will be reassured that the information they provide is confidential.
3. We will take all the usual steps to protect the confidentiality of personal information, including but not limited to dissociating identifying information from research data; using unique alpha-number coding systems that permit linkages to identifying data only via files that are stored separately; storage of data on password protected servers or computers; storage of paper data forms in locked files within locked rooms with access limited to approved research staff. All investigators and research staff are required to undergo HIPAA training and to sign a confidentiality agreement under the authority of the Human Subjects Division of the University of Washington and participating sites.

Risk Management

Loss of Confidentiality: All of the paper-based assessments will be kept in locked file cabinets at the study site. All data will be identified by a subject number. The link between participant identities and subject number will be kept separately from the study data. All personnel will receive HIPAA training as required by the University of Washington's Human Subjects Division.

XIX. Importance of Knowledge to be Gained

At the completion of this study, we will have evidence on whether Bright White Light Therapy improves sleep after TBI. If this study is successful, we will have an **immediately available, effective, non-invasive** way of improving sleep for patients who have experienced a TBI that will enhance not only sleep timing but also thinking abilities and possibly long-term recovery after TBI.

XX. Study Finances

Funding Source

This study is financed through TBI Model System Grant for the 2012-2017 Grant Cycle. This a module multi-site project that will be conducted at three locations. All participating sites have received funding from the National Institute on Disability and Rehabilitation Research.

Subject Stipends or Payments

There is no compensation planned for subjects who choose to participate in this study.

XXI. Overall Project Evaluation

Overall study data completeness, timeliness, and quality will be monitored by the study investigators. Automated data reports will be generated monthly, displaying information relevant to the milestones described in the previous section. For example, cumulative subject accrual rates, subject retention rates, inter-rater reliability, and data accuracy reports will be generated routinely to monitor progress toward goals. Progress toward study milestone will be discussed at the project meetings. Quarterly reports will be filed with the NIDRR project officer. Quarterly safety reports will be submitted to [name]. Annual reports will be filed with the TBIMS Annual Reports.

Investigators and key study personnel will meet by telephone bi-weekly prior to the initiation of the intervention to discuss progress. Investigators will meet twice yearly at the TBIMS Project Directors meeting. Site teams will meet weekly during the intervention period to discuss progress and barriers. If problems arise or tasks are not progressing as planned, [name] will work with the research team to devise an action plan. Plans will be put in writing with a timeline to correct the problem. [name] will track and follow-up on these plans. Any significant problems that would affect overall project outcomes will be reviewed with the NIDRR project officer to obtain additional assistance in developing an action plan.

Table 3: Timeline of Research Activities

	2013	2014	2015	2016	2017
Pre-Enrollment Activities					
Complete feasibility study	X				
Manual of Procedures	X				
Primary site IRB	X				
Collaborator sites IRB		X			
Research Assistant Training		X			
Rehab Staff Training		X			
Post-Enrollment Activities					
Cumulative Enrollment Target			43	86	128
Data collection		X	X	X	X
Actigraphy interpretation		X	X	X	X
Data Analysis/Dissemination					
Primary study report					X
Manuscript preparation					X

Figure 2. Project Staff Flow Chart

List of Acronyms and Abbreviations

- **ACG** = Actigraphy
- **AE** = adverse event
- **BMI** = body mass index
- **BNI-FS** = Barrow Neurological Institute Fatigue Scale
- **BWL** = Bright white light (experimental treatment condition in this study)
- **DSM** = Data safety monitor
- **GCS** = Glasgow Coma Scale
- **GOAT** = Galveston Orientation and Amnesia Test
- **KSS** = Karolinska Sleepiness Scale

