Aim 1: In persons with TBI, prospectively compare overnight sleep efficiency in a cohort exposed to morning Bright White Light with a comparison group exposed to Red Light in an acute inpatient rehabilitation setting.

Aim 2: Explore the relationship between Bright White Light exposure during inpatient rehabilitation after TBI and mood, therapy participation, attention, rate of functional recovery and length of stay.

Aim 3: Develop and describe sleep study procedures on the inpatient rehabilitation unit for persons with TBI to support optimal and feasible design of future studies in this important area.

Research Hypothesis:

In persons with TBI, prospectively compare overnight sleep in a cohort exposed to morning Bright White Light with a comparison group exposed to Red Light in an acute inpatient rehabilitation setting.

Hypothesis 1: Individuals exposed to Bright White Light for 30 minutes each morning will have better sleep compared to the Red Light exposure group, as measured by sleep efficiency.

Hypothesis 2: Individuals with daily morning Bright White Light exposure will have better mood (as measured by the Positive and Negative Affective Schedule, PANAS), therapy participation (as measured by a 0-100 therapist rating) and attention (as measured by the Symbol Digit Modalities Test) at 10 days compared to individuals with daily Red Light exposure. The group exposed to Bright White Light will also have less daytime sleepiness and fatigue (as measured by the Karolinska Sleepiness Scale (KSS) and the Barrow Neurological Institute Fatigue Scale (BNI-FS), a faster rate of functional recovery as measured by FIM™ efficiency for the rehabilitation stay and a shorter length of stay compared to those in the Red Light group

Hypothesis 3a: Bright White Light exposure will be rated as a reasonable addition to clinical care by staff using Likert scale ratings. Categorize and quantify rates of any side effects of Bright White Light and Red Light exposure in persons with TBI during inpatient rehabilitation.

Hypothesis 3b: Bright White Light and Red Light exposure will be generally well tolerated with side effect profiles and rates similar to those observed in previous studies with other populations.

[figure not shown]
See Appendix for Flowchart on Specific Aims of this study

V. Study Description

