5. Past medical history of narcolepsy
6. Past medical history of bipolar disorder
7. Past medical history of obstructive sleep apnea (OSA)
8. Sleep disturbance defined as having a "0" rating by research staff (using all sources available). If rated a "0" for no sleep disturbance, they must also NOT be receiving sleep medications in the last 72 hours
9. Suspected diagnosis of obstructive sleep apnea (determined by the Berlin Questionnaire)
10. Tetraplegia with less than antigravity strength in all myotomes caudal to C6 level given the limitations on measuring movements with actigraphy in this population (i.e. cannot reliably detect upper extremity or lower extremity movement with this level of paralysis).
11. Current medical orders indicated for night time sleep disruption (e.g. chest PT, MIE q2 hours of meds that disrupt sleep). *May be re-approached if the medical orders are no longer in place.

IX. Rationale for Study Population

The study population of interest is TBI in the setting of acute inpatient rehabilitation, which is typically moderate to severe TBI. Persons less than 18 years of age or greater than 70 years are being excluded from the study because of baseline sleep physiology differences seen in younger and advanced ages. We wish to enroll those with sleep disturbances; those with normal sleep will not be enrolled. We are excluding those who would not benefit from light exposure due to eye abnormalities or those with other pathology that will interfere with sleep and cannot be affected by light exposure. Additionally, since actigraphy relies on limb movement for recording, those with tetraplegia would be excluded.

X. Data Collection and Measures

Screening of subjects will need to occur to determine eligibility of subjects, including review of medical chart. If patients are not eligible or are excluded based on exclusion criteria, no identifiable data is retained. Once consented into the study, the exclusion criteria will be reviewed with the patient and/or their legal representative. Data collection measures, areas assessed, and the timing of when this data is collected is shown in Table 1.

Table 1: Data Collection Measures and Areas Assessed

Measure	Area to be Assessed	Screening and Baseline (Day 0-2)	Intervention (Days 3-12)	Outcome (Day 13)
Demographics	Characteristics (age, education, gender)	X		
Injury characteristics	Cause of injury, date of injury, lowest GCS, PTA/GOAT	X		

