Day 0-1 (2 days): After determining eligibility, the participant will be fitted with an Actiwatch (actigraphy) for continuous monitoring of activity levels both during the day and night (American Sleep Disorders Association, 1995). The Actiwatch will be worn continuously (with removal as needed for hygiene, shower or other clinical care) from enrollment to outcome measurement. Actiwatches will be fully charged and cleared of all previous data before being provided to a subject. Units will be set to record activity data in 60-second epochs. Actiwatches have sufficient built-in memory capacity and battery life to be used for approximately 30 days without recharging. Additionally, sleep logs that rate patient sleep are filled out every hour, between the hours of 2200-0600, this information is then obtained

as completion of the Makley scale. A complete review of symptoms and medical history will be obtained from the subject, LAR, and medical records.

Day 2: Baseline data collection is obtained (See Appendix for Baseline Data Collection Forms). Measures collected include: Symbol Digit Modalities Test, Positive and Negative Affect Schedule (PANAS), Barrow Neurological Fatigue Scale. Clinical Staff, will be asked if there was sleep difficulties and therapist will be asked to rate therapy participation for that day.

Day 2: Randomization. After baseline testing is completed, subjects will be randomized (50:50) using a 2-level stratification design based on two pieces of information:

- 1) Center (U. Washington-Seattle, Baylor-Dallas, Mount Sinai-New York) and
- 2) Severity of Sleep Disturbance using Delirium Rating Scale-Revised 98 Item 1

The rating for the Delirium Rating Scale Item 1 are: 1=Mild, 2=Moderate, 3=Severe

(Nakase-Richardson R S. M., Prospective evaluation of the nature, course, and impact of acute sleep abnormality following TBI , 2013) Using an Access Database, developed by [name] at the University of Washington, centers will randomize the participant into either the Bright White Light Group or the Dim Red Light Group. [46]

Light Therapy:

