Appendix

- Inclusion/Exclusion Checklist
- Makley Sleep Scale Form
- Berlin Questionnaire
- Del-R-98, Question 1 Form
- Functional Independence Measure (FIM)TM
- PANAS
- Karolinska Sleepiness Scale
- Barrow Neurological Institute Fatigue Scale
- Quarterly Staff Survey (a.k.a. Clinician Feasibility Survey)
- Overview of Study Figure

TWILIGHT Study Inclusion and Exclusion Checklist

Inclusion Criteria

Must meet all of the criteria below

- Have experienced a moderate to severe TBI. Defined by any of the following:
 - 1) Loss of Consciousness greater than 30 minutes.
 - 2) Emergency Room admission with a Glasgow Coma Scale of 12 or below.
 - 3) Intracranial abnormalities on imaging.
 - 4) Post-traumatic amnesia that lasts more than 24 hours.
- Admitted to acute inpatient rehabilitation unit at Harborview Medical Center within 3 months of their Traumatic Brain Injury.
- Able to communicate in English.
- Between the ages of 18 and 70 years old

Exclusion Criteria

Unable to enroll if any of the following are true

- Complete blindness
- Absence of eye opening or disorders of consciousness (Rancho level 1-3)
- Does not have sleep disturbance (rating of "0" on item one of the *DeIRS-R98*. If has a rating of "0", but if taking sleep medication in the last 72 hours, then include)
- Tetraplegia with less than antigravity strength in all myotomes caudal to C6 level given the limitations on measuring movements with actigraphy in this population (i.e. cannot reliably detect upper extremity or lower extremity movement with this level of paralysis).
- Past medical history of retinal pathology
- Past medical history of light sensitivity
- Past medical history of narcolepsy
- Past medical history of bipolar disorder
- Past medical history of obstructive sleep apnea
- Suspected sleep apnea. (Determined by administering the Berlin questionnaire)
- Current medical orders indicated for night time sleep disruption (e.g. chest PT, MIE q2 hours of meds that disrupt sleep)". For these subjects, may re-approached if the medical orders are no longer in place.

TWILIGHT STUDY

Was watch verified as on? Staff Initials _____

Date: _____

Makley Sleep Scale Form Clinician rating

Time	Rounding Initials	Sleep Rating Given Observation in the Last Hour (circle)			
2200		0	1	2	3
2300		0	1	2	3
0000		0	1	2	3
0100		0	1	2	3
0200		0	1	2	3
0300		0	1	2	3
0400		0	1	2	3
0500		0	1	2	3
0600		0	1	2	3
Ratings:		Asleep	Drowsy/falling asleep	Drowsy/waking up	awake

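### Hypothesis 3b judges tolerability only against rates from other populations, and Section XII plans no side-effect comparison between the randomised arms

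*Combined protocol and SAP*

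**What the plan says.** - Section IV, Hypothesis 3b, applies one yardstick to both lights: "side effect profiles and rates similar to those observed in previous studies with other populations". It gives no rate, margin or source study.
- Section IV, Hypothesis 3a, sets a descriptive task in both arms: "Categorize and quantify rates of any side effects of Bright White Light and Red Light exposure in persons with TBI during inpatient rehabilitation".
- Section XVIII, Potential risks, says that the effects of bright light "can include hypomania, irritability, headache, nausea, eye strain or vision changes and sleep changes". It gives no frequencies.
- Section IX describes the intended population: "We wish to enroll those with sleep disturbances; those with normal sleep will not be enrolled". The Appendix checklist adds an exception for a patient rated 0 on the sleep item: "but if taking sleep medication in the last 72 hours, then include".
- Section XV counts a symptom as an AE if it is new or gets worse during the study. Section XVI adds a five-level grade of relatedness. Its Possibly Related level covers events that either the treatment or the patient's clinical state could have caused.
- Section XI randomises patients 1:1 to BWL or dim RL.
- Section XII covers sleep efficiency, the secondary outcomes, FIM efficiency, length of stay and a description of nursing burden. It names no side-effect analysis.

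**The concern.** The tolerability statement would rest on comparing recently injured inpatients with people who differ from them in diagnosis, phase and setting. If the observed rates are higher, the reader cannot tell whether the light or the injury is responsible. If they look similar, the reader cannot tell whether a light effect is hidden by differences between the populations.

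The protocol accepts this reasoning elsewhere. Section VII discounts the effect size from a chronic-TBI pilot because phase, setting and treatment length differ. Section III says that evidence on tolerance of bright light in this population is limited. The randomised RL arm can supply a comparison within the right population, but no analysis uses it for side effects.

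**Working it through.** **1. The plan's own figure.** Hypothesis 3b has no stated number. The only computed design figure is the sample size in Section VII: effect size 0.5, 80% power, 64 per group. Alpha is not stated, and two-sided 0.05 is assumed here. The normal approximation gives 2 × (1.96 + 0.842)² / 0.5² = 62.8, or 63 per arm. The t-test calculation gives 63.77, or 64 per arm, with power 80.1%. So 128 is reproduced, and 64 per arm is used below.

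**2. Where light and injury overlap.**
- Sleep changes are a listed side effect (Section XVIII), and sleep disturbance is the intended entry condition (Section IX). This is the one overlap that the documents establish through eligibility.
- A stable disturbance present at entry is not an AE under Section XV. A worsening or fluctuation caused by the injury can be one.
- Relatedness grading removes some of these events but not all, because Possibly Related admits either cause.

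**3. What each comparison estimates.** Let r be the rate caused by light, equal to the external rate. Let b be the additional background rate from the injury that is still counted as a side effect after grading. Assume that the two act independently.
- Observed rate = 1 − (1 − r)(1 − b) = r + b(1 − r).
- Excess over the external rate = b(1 − r), which is zero only if b = 0.
- With light-caused rates r_B (BWL) and r_R (RL) and the same b in both arms by randomisation, BWL minus RL = (r_B − r_R)(1 − b). This is zero whenever the two lights are alike, whatever b is.

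The documents give neither r nor b. For illustration only, with r assumed to be 10%:

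| Assumed b | Observed rate | Apparent excess |
|---|---|---|
| 0% | 10% | 0 points |
| 10% | 19% | 9 points |
| 20% | 28% | 18 points |
| 30% | 37% | 27 points |

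The table shows the mechanism. It does not estimate the bias.

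**4. Precision of the arm contrast.** The 95% half-width is 1.96 × √(2p(1 − p)/64) at a common rate p (assumed):

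| p | Half-width |
|---|---|
| 5% | 7.6 points |
| 10% | 10.4 points |
| 20% | 13.9 points |
| 30% | 15.9 points |

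At RL rates of 5%, 10%, 20% and 30%, the difference detectable with 80% power (two-sided 0.05) is about 17, 20, 23 and 24 points. With equal rates in both arms, the chance of a false BWL excess is 2.2% to 2.6% for common rates from 10% to 50%.

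**The case against.** The strongest reply is that Hypothesis 3b is a descriptive expectation with safeguards around it. It has no margin or decision rule. The AE definition excludes stable pre-existing symptoms. Investigators grade relatedness, and the Unlikely level covers events with a better alternative explanation. Hypothesis 3a already yields rates in both arms, and an independent monitor reviews safety every quarter. Hypothesis 3b also asks whether both lights are tolerated, and a BWL minus RL difference cannot show harm common to both.

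Much of this stands, and it rules out several stronger inferences that a reader might draw:
- **That every enrolled patient already has the listed side effects.** Only sleep changes are tied to eligibility, and the sleep-medication exception makes that nearly all rather than all. The documents do not say that enrolled patients have headache, irritability, nausea or visual symptoms.
- **That a formal test will fail.** None is specified.
- **That the 86% with sleep abnormality in Section X.B measures the bias.** It is a prevalence at admission, whereas AEs count new or worsening symptoms.
- **That an excess with bright light would go unseen.** Rates in both arms are to be quantified. What is missing is a planned difference with its uncertainty.

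The reply does not rescue the comparator. Injury-related worsening can still be recorded as an AE, grading leaves the cause open in some cases, and individual attribution does not replace a randomised contrast. Without a margin, almost any result could be read as similar.

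**Conclusion.** The point holds in a limited form. The only comparator named for tolerability is external and cannot separate light effects from the course of TBI, while the randomised comparator has no planned side-effect analysis. The documents give no external or background rates, so the direction and size of any error in a particular symptom cannot be stated. The rates in the working are assumptions.

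The contrast removes background common to the arms, subject to the usual chance imbalance. It measures BWL relative to RL, not relative to no light. The primary and secondary efficacy analyses are not affected.

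**What to change.** Add to Section XII:
- By assigned arm, the number and proportion of randomised patients with any recorded AE, and with each side effect listed in Section XVIII, regardless of graded relatedness.
- The BWL minus RL difference in each proportion, with a 95% CI, presented as estimation.

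Reword Hypothesis 3b to match. Keep the per-arm rates and the published rates as descriptive context for general tolerability, because the contrast cannot show harms common to both lights.

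The cost is mainly wording. Section XVI already requires specific questioning at each contact and a record of the type, dates and severity of each event, so no new symptom instrument is needed. Someone must map recorded events to the listed side effects. Section XVI groups related symptoms under one diagnosis, so some will have to be found in the source document. The main downside is precision: the plan should say that intervals will be wide and that rare events will stay unresolved.
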